# 1. STUDY SUMMARY

Full Title:	INFINITY™ with ADAPTIS™ and EVERLAST™ technology total ankle replacement follow-up			
Short Title:	UK ADAPTIS™ Study			
Phase:	Phase 4, Post-Market			
Design:	A prospective multi-centre cohort series of INFINITY™ with ADAPTIS™ and EVERLAST™ Technology with Poly Insert for patients requiring primary total ankle replacement (TAR) i.e. Total Ankle Arthroplasty (TAA).			
	Patients meeting the criteria for the study will be asked to enrol by providing written informed consent.			
	The patients will be monitored clinically by post-operative follow-up examinations and Patient reported outcome measures (PROMs) (Manchester Oxford Foot & Ankle Questionnaire (MOXFQ), Ankle Osteoarthritis Scale (AOS), EQ5D-5L).			
Duration:	The study will have a minimum 12-month recruitment period and up to 5 years post-operative follow-up.			
Setting:	It is anticipated around 10 UK NHS Hospital Trusts regularly performing TAA/TAR will participate.			
Sample Size:	Minimum of 200 patients.			
Inclusion Criteria:	
 
Male or non-pregnant female over the age of 21 years with a diagnosis of end stage ankle arthritis and requiring primary TAA/TAR and is suitable for the use of the ADAPTIS TAA/TAR.
 
Patients who are physically and mentally willing and able to comply with the post-operative follow-ups and an appropriate rehabilitation schedule.
 
Patient can understand and provide written consent.
 
			
Exclusion Criteria:	
 
Patients with previous ankle arthrodesis or Patients who require revision of previously implanted TAA/TAR.
 
Any patients presenting with clinically relevant conditions prior to implantation, that would contraindicate implantation of a TAA/TAR.
 
			

Indication:	Intended use: It is intended to give a patient limited mobility by reducing pain, restoring alignment, and replacing flexion and extension movement in the ankle joint.				
	Indications for use:				
	
 
Patients with ankle joints damaged by severe rheumatoid, post-traumatic, or degenerative arthritis.
 
				
	
 
Patients with a failed previous ankle surgery.
 
				
Intervention:	INFINITY™ with ADAPTIS™ and EVERLAST™ technology with Poly Insert for patients requiring primary TAA/TAR.				
Objectives:	The primary objectives of the study are to assess device survivorship and performance using rates of re-operation or revision and PROMs over a 5-year post-operative period.				
Outcomes:	Primary outcomes are functional status (MOXFQ) at 2-year post-operative and device survivorship at 2 years.				
	Secondary outcomes are:				
	
 
Survivorship of the components at 2 years and 5 years post-operative.         
 
Revision of any components (excluding incidental polyethelene exchange for infection).
 
Re-operation without component exchange.
 
Type and frequency of adverse events (AEs), specifically operative and device related AEs and serious AEs (SAEs).
 
 
 
				
	
 
Functional status, pain and disability (MOXFQ & AOS), and health-related quality of life (EQ5D-5L) at 6 months, 1 year, 2 years, and 5 years post-operative.
 
				
	
 
Clinical assessment at 6 weeks, 6 months, 1 year, 2 years, and 5 years.
 
				
	
 
Radiographic assessments at 6 months,1 year, 2 years, and 5 years.
 
				
Analysis of Results:	The analyses will be mainly descriptive. Continuous data will be summarised using means and standard deviations (or median, interquartile range, minimum and maximum as appropriate). Categorical data will be summarised using counts and percentages. Linear or logistic regression models (as appropriate depending on the outcome) will be used to				

evaluate the influence of patient, clinical and surgical factors on outcomes.

AEs and SAEs will be summarised descriptively, whether they are operative or device related.

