# 3. STUDY PURPOSE

An ankle replacement procedure consists of replacing the worn-out joint surfaces of the ankle with metal and plastic components that are shaped to allow continued movement of the ankle. There are several different types of ankle replacement available. Infinity ankle implants are already routinely used in NHS hospitals. The INFINITY™ with ADAPTIS™ and EVERLAST™ ankle replacement system is a development of the Infinity ankle implant, designed to attach to the bone better and to wear out more slowly.

The purpose of the UK ADAPTIS™ Study is to assess the performance and function of the newly introduced INFINITY™ with ADAPTIS™ and EVERLAST™ technology Total Ankle System for total ankle replacement (TAR) or arthroplasty (TAA) and EVERLAST™ Poly Insert that modernises and streamlines Stryker's TAA/TAR portfolio.

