### 8. DEVICE DESCRIPTION

The INFINITY™ with ADAPTIS™ and EVERLAST™ technology Total Ankle System is a two-piece semi-constrained fixed-bearing, bone-sparing total ankle prosthesis that restores mobility to a failing ankle joint. The System consists of a highly polished metal talar dome, a titanium alloy tibial tray, and Poly Insert (an ultra-high molecular weight polyethylene tibial insert). The components are available in a variety of sizes and design configurations intended for both primary and revision applications.

Through the advancement of partial and total joint replacement implants, the surgeon has been provided with a means of restoring mobility, correcting deformity, and reducing pain for man patients. While the prostheses used are largely successful in attaining these goals, it must be recognised that they are manufactured from a variety of materials and that any joint replacement system, therefore, cannot be expected to withstand activity levels and loads as would normal healthy bone. In addition, the system, including the implant/bone interface, will not be as strong, reliable, or durable as a natural human joint.

This system is manufactured according to International Conference on Harmonisation (ICH) Good Clinical Practices (GCP) in accordance with applicable Good Manufacturing Practices (GMP) and ISO 14155:2020 through relevant manufacturing and related validation processes.

The INFINITY™ with ADAPTIS™ and EVERLAST™ technology Total Ankle System Tibia Tray and Talar Dome are manufactured using an improved process known as Direct Metal Laser Sintering, also known as ADAPTIS™ 3D printing, produces a porous metal surface made from Ti6Al4V (Tibia Tray) and CoCr (Talar Dome), respectively, to interface with the bone.

The INFINITY™ with ADAPTIS™ Technology modular articular inserts are manufactured from EVERLAST™ Highly Crosslinked Polyethylene blended with Vitamin E. The propriety manufacturing process has been optimised to develop an enhanced ankle insert with retained material strength, reduced oxidation potential, and improved wear resistance. They are available in 8 sizes, with 4 thicknesses per size.

The INFINITY™ with ADAPTIS™ and EVERLAST™ technology Total Ankle System includes:

- INFINITY™ with ADAPTIS™ Technology Tibial Tray
- INFINITY™ with ADAPTIS™ Technology Chamfer-Cut Talar Component
- INFINITY™ with ADAPTIS™ Technology Flat Cut Talar Dome
- INFINITY™ EVERLAST™ Poly Insert

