# 9.1.5 INTRA-OPERATIVE EVALUATION

- 1. Surgery date
- 2. Operative side
  - a. Left
  - b. Right
- 3. Anaesthesia Class and Type
  - a. General
  - b. Regional, Epidural
  - c. Regional, Nerve Block
  - d. Regional, Spinal
  - e. Other
- 4. Duration of surgery
  - a. Hours/Mins
- 5. Intra-operative AEs
  - a. Yes
    - i. Fracture
    - ii. Nerve or Vessel Injury
    - iii. other
  - b. No

- 6. Components used and sizes
- 7. Patient Specific or Standard Instrumentation (PSI)

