### 11.2 STATISTICAL ANALYSIS PLAN

The analyses will be mainly descriptive. Continuous data will be summarised using means and standard deviations (or median, interquartile range, minimum and maximum as appropriate). Categorical data will be summarised using counts and percentages. Graphs will be produced to display trajectories in outcomes over time. Linear or logistic regression models (as appropriate depending on the outcome) will be used to evaluate the influence of patient, clinical and surgical factors on outcomes.

AEs and SAEs will be summarised descriptively and using graphs by whether they are operative, or device related.

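### Surgical-factor regression is planned for a newly introduced implant, but the listed data omit the operating surgeon and prior cases with it, so surgeon effects can be only partly removed

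*Protocol*

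**What the plan says.** The analysis paragraph appears in the Study Summary (section 1) and again in section 11.2. It promises regression, linear or logistic according to the type of outcome, in order to "evaluate the influence of patient, clinical and surgical factors on outcomes". It is the only modelling the protocol names. The other analyses are described as mostly descriptive.

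Section 9.1.5 lists seven intra-operative items: surgery date, side, anaesthesia, duration, intra-operative adverse events, "Components used and sizes", and whether instrumentation was patient-specific or standard. Section 8 offers two talar designs, a chamfer-cut component and the "INFINITY™ with ADAPTIS™ Technology Flat Cut Talar Dome", so component choice is a real surgical variable.

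Section 3 says the study is to "assess the performance and function of the newly introduced" system. It also says that "Infinity ankle implants are already routinely used in NHS hospitals" and describes the new system as a development of that implant. Section 1 expects around 10 Trusts that regularly perform ankle replacement. The number of surgeons is not given.

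**The concern.** The surgical factors available to the regression are those in 9.1.5. Instrumentation and talar design may reflect who operates. Where they do, a coefficient for instrumentation also carries differences between surgeons and, with a new implant, differences between a surgeon's early and later cases.

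None of the forms in sections 9.1.1 to 9.1.8, 10.1 or 10.2 lists the operating surgeon, grade, or number of earlier implantations. The one form item that mentions a surgeon is the pre-operative radiographic report in 9.1.3, and it has no identity or experience field. This is a matter of what is collected, so a later analysis plan can choose a better model but cannot adjust for a field that nobody recorded.

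At stake is a published association between instrumentation or component and outcome that is partly or wholly a surgeon effect.

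**Working it through.** The protocol gives no figure to reproduce on this point. The check of the form lists is set out above. What follows only illustrates possible size, and **every input except the 200 patients (section 6.1) and the 10 sites (section 1) is assumed**.

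**MOXFQ.** Assume 10 sites with 2 surgeons each and 10 patients per surgeon. Each surgeon is experienced with probability 1/2, experience shifts the score by 8 points, the residual SD is 20, and instrumentation has no true effect. Let experienced surgeons use patient-specific instrumentation in a proportion p of cases and inexperienced surgeons in 1 − p, a gap of d = 2p − 1.

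- No adjustment: bias ≈ 8d.
- Site adjustment: the within-site variance of experience is 1/8, and that of instrumentation is p(1−p) + d²/8. Bias ≈ 8 × (d/8) / (p(1−p) + d²/8) = d / (p(1−p) + d²/8).
- Surgeon fitted: expected bias is 0.

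| Use, experienced / inexperienced | d | Unadjusted: formula, simulated | Site-adjusted: formula, simulated | Surgeon fitted: simulated |
|---|---|---|---|---|
| 60% / 40% | 0.2 | 1.6, 1.52 | 0.2/0.245 = 0.82, 0.81 | −0.07 |
| 80% / 20% | 0.6 | 4.8, 4.68 | 0.6/0.205 = 2.93, 2.90 | −0.10 |
| 95% / 5% | 0.9 | 7.2, 7.11 | 0.9/0.14875 = 6.05, 6.10 | 0.15 |

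The simulated values are means of 2,000 runs. Site adjustment removes (1.52 − 0.81)/1.52 = 47%, (4.68 − 2.90)/4.68 = 38% and (7.11 − 6.10)/7.11 = 14% of the bias. It helps least where instrumentation follows the surgeon most closely.

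**Cost in precision.** With residual SD 20, the standard error of the instrumentation effect is about 20/√(200 × 0.25) = 2.8 points without adjustment. With surgeon fitted it is about 20/√(200 × p(1−p)), ignoring lost degrees of freedom:

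- 60/40: 20/√48 = 2.9
- 80/20: 20/√32 = 3.5
- 95/5: 20/√9.5 = 6.5

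**Revision.** Assume 2-year revision of 2% for experienced and 6% for inexperienced users, who share the cases so that 80% of patient-specific and 30% of standard operations are by experienced users.

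- Patient-specific: 0.8 × 2% + 0.2 × 6% = 2.8%.
- Standard: 0.3 × 2% + 0.7 × 6% = 4.8%.
- Spurious risk ratio: 2.8/4.8 = 0.58.

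With 3% and 6%, and 60% and 40%, the rates are 0.6 × 3% + 0.4 × 6% = 4.2% and 0.4 × 3% + 0.6 × 6% = 4.8%, a ratio of 0.875.

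With 100 patients per group, the first case expects 2.8 and 4.8 revisions. The SE of the log ratio is √(1/2.8 − 1/100 + 1/4.8 − 1/100) = 0.74, so the 95% interval runs from about 0.14 to 2.5. The assumed bias is smaller than the sampling noise.

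**The case against.** Several points on the other side stand.

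- **The learning curve may be short.** The predecessor is in routine use, sites regularly perform the procedure, and the described changes concern bone attachment and wear, with no new technique stated. Differences between surgeons could still exist.
- **The premise is unsupported.** Nothing in the protocol says that instrumentation or talar choice follows surgeon habit. Without such a link there is no spurious effect.
- **Partial adjustment is possible.** Site is known and surgery date gives case order within a site. That settles surgeon identity where a Trust has one operating surgeon. The local identification log (6.4), access to medical records (13) and consent to registry linkage (6.3) might recover the surgeon later, though none is planned for this purpose. A reader might infer that surgical factors cannot be separated from the surgeon at all. The documents support only that they cannot be fully separated with the listed fields.
- **Section 9.1 is not a full data dictionary.** It lists no site field either, although sites are plainly identifiable. REDCap may already hold a surgeon field.
- **Event-level attribution is planned.** A reader might infer that the study cannot tell a device problem from early-case failures. Section 10.1 codes technical error, subsidence, aseptic loosening and implant failure, and its re-operation codes mention malposition. This is imperfect, but it gives some separation.
- **Covariates are not yet fixed.** Section 11 defers a detailed analysis plan, so model form is properly left to it. The missing data field is not.

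**Conclusion.** The point holds as a modest gap in data collection for a stated secondary analysis. A reader might go further and infer that the 2-year MOXFQ and survivorship results are compromised. They are not: both primary outcomes (section 5.2) describe the cohort as operated on, and a surgeon code would not change either estimate.

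The size is unknown from the documents. Under the assumptions shown, the spurious MOXFQ effect ranges from 1.5 to 7.1 points unadjusted, and 0.8 to 6.1 points remain after site adjustment. The practical exposure is mainly in the MOXFQ models, because revisions are likely to be too few for a surgical-factor model to say much either way. The conclusion rests on instrumentation or component choice varying by surgeon, on some Trusts having more than one operating surgeon, and on the listed fields being those collected.

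**What to change.** Add two items to section 9.1.5, or confirm that REDCap already holds them:

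1. a pseudonymised operating-surgeon code, with the key held at site;
2. that surgeon's running number of implantations of this system, counting cases before the study.

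Then state in section 11.2 and the Study Summary that surgical-factor models account for surgeon and case order where event numbers allow, and that otherwise the associations are reported as unadjusted for surgeon.

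The cost is two fields that can be recorded at each operation and a minor form amendment, with no extra visits or patients. Intervals for surgical factors will widen. In the illustration the standard error rises from 2.8 to between 2.9 and 6.5 points. If instrumentation is almost constant within surgeon, the honest result may be that its effect cannot be estimated from this cohort.

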# 2. EVALUATION SCHEDULE

Evaluation	*Pre- Op	Intra- Op	**6 weeks	6 months	1 year	2 years	5 Years
Time Window	N/A	N/A	+/- 2weeks	+/- 2weeks	+/- 6weeks	+/- 3months	+/- 6months
Inc./Exc. Criteria	Х						
Pre-Op Clinical History	X						
Intra-Op Surgical Details		Х					
Clinical Follow- Up			X	Х	X	x	х
MOXFQ	Х			Х	Х	Х	Х
AOS	Х			X	X	X	Х
EQ5D-5L	Х			Х	Х	Х	X
Radiographs	Х			Х	Х	Х	Х
Adverse Events or Termination	Anytime						

\*Pre-Op: Date of or any time post the date of written informed consent up to 6 months prior to date of surgery.

If Patients exceed a 6 month wait for surgery, a radiograph will be repeated at their pre-operative assessment or on the morning of surgery as part of routine care.

Patient study consent will be valid for the 12 months from the date of consent unless withdrawn.

\*\*6 Weeks: This is not an additional study-related clinical visit. Research teams will be required to review the 2- and 6-week clinical visits that occur as standard of care to report any adverse events.

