### 4. STUDY DESIGN

This is a prospective multi-centre cohort study of INFINITY™ with ADAPTIS™ and EVERLAST™ technology Total Ankle System TAA/TAR implantations.

Patients meeting the criteria for the study will be invited to enrol by providing written (electronic) informed consent.

The patients will be monitored clinically by post-operative follow-up examinations and patient reported outcome measures (PROMs).

The length of the Patient follow-up schedule in the study is based on the previously published UK INFINITY™ Study¹.

The study is set up to record data pre-operative, intra-operative, and at 6 weeks, 6 months, 1 year, 2 years, and 5 years post-operative.

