### 9.1.6 POST-OPERATIVE CLINICAL HISTORY

- 1. Follow-up timepoint
  - a. 6 weeks
  - b. 6 months
  - c. 1 year
  - d. 2 years
  - e. 5 years
- 2. Date of assessment
- 3. Has the patient experienced any post-operative AE/SAEs
- 4. Radiograph (not required for 6 weeks)
  - a. CT

This data will be used if indicated as part of clinical care, and therefore it may not be available for all participants

- b. Plain radiograph
- c. Radiographic reporting template

  The purpose of the post-operative radiographic evaluations will be to assess, record, and report for migration, loosening, subsidence of the device, any osteolysis and cyst formation.

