## 10. ADVERSE EVENTS AND DEVICE REMOVAL EVENTS

The PI and research delivery team at each site are required to document all AEs and SAEs occurring within a 90-day post-operative period including date of occurrence, type of AE/SAE, treatment and outcome. Following this, only AE/SAEs relating to the ankle joint or related structures (i.e., ankle and surrounding structures, Achilles tendon, calf muscle, hindfoot and midfoot proximal to mid metatarsals) need to be reported.

All AEs and SAEs will need to be reported to the study management team and to host Research & Development (R&D) department according to local guidelines. Any unanticipated device of study related SAEs will need to be notified to the HRA and REC.

An SAE report form should be completed by the PI and research delivery team within 24 hours of the site's knowledge.

The PI will keep a copy of the AE/SAE information in their electronic Investigator Site File (eISF) at their site. If at the time of sending the report, all details are not available, then one must send it with the available data and then seek to obtain complementary information. The complementary information will be sent by the PI or research delivery team of the study site to the sponsor, Northumbria Healthcare NHS Foundation Trust, and study management team, South Tees Hospitals NHS Foundation Trust, as soon as it will be available.

In case of component revisions product related issues and/or SAEs, Stryker will be notified of the event.

Death will be both reported in the SAE report form and in the termination form part of the CRFs.

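### All AEs must be documented to day 90, but no active AE review is scheduled between the 6-week visit and 6 months

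*Protocol*

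**What the plan says.** Section 10 sets two reporting scopes, divided at day 90. Sites must "document all AEs and SAEs occurring within a 90-day post-operative period". After that the scope narrows: "Following this, only AE/SAEs relating to the ankle joint or related structures" need reporting. SAE timing is driven by awareness: "An SAE report form should be completed by the PI and research delivery team within 24 hours of the site's knowledge".

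Section 4 places data collection "at 6 weeks, 6 months, 1 year, 2 years, and 5 years post-operative", so no time point lies at or near day 90. In section 2 the windows are two weeks either side for both the 6-week and the 6-month visits. The footnote to the 6-week column explains that this is not an extra study visit, and gives the task: "Research teams will be required to review the 2- and 6-week clinical visits that occur as standard of care to report any adverse events". The AE row of the same schedule is not tied to any visit: "Adverse Events or Termination Anytime".

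The post-operative form in section 9.1.6, used from 6 weeks to 5 years, carries one AE item: "Has the patient experienced any post-operative AE/SAEs". It states no recall period and does not mention the change of scope at day 90. Each event then has its own form (section 10.1), whose first field is the event date.

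**The concern.** The duty to document runs to day 90, but scheduled active review stops at about day 42 and resumes only at about 6 months. The rule that AEs may be entered at any time, and the 24-hour SAE clock, say when a known event is reported. Neither says how the site comes to know of it.

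The events at risk are those away from the ankle that occur between the 6-week review and day 90. The protocol chose to count such events: section 7.1 lists medical complications among the risks, and section 10.1 has codes for deep vein thrombosis, pulmonary embolism and death. Some may be treated outside the orthopaedic clinic, so the research team may not hear of them at the time.

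Two uses of the data depend on this. Type and frequency of AEs and SAEs is secondary outcome 1c in section 5.3. The ongoing safety review in section 11.1 informs the decision on whether the study and implantation continue. Missed events lower the first, and late events weaken the second. An analysis plan cannot recover events that were never elicited.

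**Working it through.** The protocol states no figure for this gap, so there is nothing to reproduce. The check is day arithmetic on its own time points.

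**Inputs**
- All-event window: 90 days (section 10).
- Last scheduled AE review before 6 months: week 6, two weeks either side, so day 42 with a range of day 28 to day 56 (section 2).
- Next scheduled contact: 6 months, two weeks either side (section 2). Six months is taken as 365.25 / 2 = 182.6 days.

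**Step 1. Part of the 90-day window after the last scheduled review**

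Uncovered share = (90 − day of review) / 90.

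| 6-week review held on | Days left to day 90 | Share of window |
|---|---|---|
| Day 28 (week 4) | 62 | 68.9% |
| Day 42 (week 6, nominal) | 48 | 53.3% |
| Day 56 (week 8) | 34 | 37.8% |

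The share exceeds one half only if the review falls before day 45 (45 / 7 = 6.4 weeks). It is therefore just over half at the nominal date, but not throughout the permitted window.

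**Step 2. When the next scheduled contact falls**
- Earliest: 182.6 − 14 = 168.6. Latest: 182.6 + 14 = 196.6. That is about day 168 to 197.
- Time since the 90-day window closed: 168.6 − 90 = 78.6 days to 196.6 − 90 = 106.6 days, or about 79 to 107 days.
- Gap from the nominal 6-week review to the nominal 6-month visit: 182.6 − 42 = 140.6 days.

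**Step 3. Delay for one event**

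An event on day 60 that nobody reports to the site would first be asked about 168.6 − 60 = 108.6 to 196.6 − 60 = 136.6 days later. For an SAE, the 24-hour clock would start only then.

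**Step 4. Which events are exposed**
- Ankle-region events: reportable both before and after day 90, and asked about at every later visit. Less exposed.
- Non-ankle events up to the 6-week review: covered by the 2- and 6-week reviews.
- Non-ankle events from then to day 90: required by section 10, with no active review until 6 months. Exposed.

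**The case against.** The strongest reply is that days 43 to 90 are not left uncovered. The AE row in section 2 is open throughout, section 10 places a standing duty on the site, and the 6-month form asks about any post-operative AE or SAE without a recall limit. In a post-market cohort under routine care, event-driven reporting plus a later question is a recognisable design choice. Outcome 1c and section 11.1 are directed mainly at operative and device-related events, and ankle-region events have no day-90 cut-off. All of this stands, and it limits the point to non-ankle events.

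Several stronger readings are tempting, but the protocol does not support them:
- *Nothing is planned to capture events after week 6.* The open AE row and the 6-month question contradict this.
- *A day-60 non-ankle event disclosed at 6 months is no longer reportable.* Section 10 sets scope by when the event occurs, not by when it is learned, so it must still be documented.
- *Events before and after day 90 cannot be told apart.* The AE form records a date. The difficulty is in eliciting events, not in dating them.
- *AE rates will be presented as complete to day 90.* Neither section 5.3 nor section 11.2 says so.
- *The share of days is the share of events missed.* Events need not be spread evenly over the window, and those after the 6-week review are not all lost.

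The reply does not show how a site would learn, before 6 months, of a non-ankle event treated elsewhere. It also leaves staff at 6 months to remember that a wider scope applied to the earlier period. Those two gaps remain.

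**Conclusion.** The concern holds as a mismatch between the 90-day documentation duty and the scheduled review. It is a weakness in ascertainment, not a contradiction in the text. Between 34 and 62 days of the window, 48 (53%) at the nominal visit, fall after the last scheduled active review, and the next contact comes about 79 to 107 days after the window closes. For that stretch, capture of non-ankle events, including SAEs managed away from the clinic, rests on spontaneous reports and on recall at 6 months.

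The likely direction is under-counting and late notice. Its size cannot be estimated, because the protocol gives neither the timing of such events nor the completeness of spontaneous reporting. The day counts assume that the 6-week review is held within its window and that 6 months is about 182.6 days. The co-primary outcomes, MOXFQ and device survivorship at 2 years, are not affected by this point. The change should be made because it is cheap and improves both outcome 1c and the section 11.1 review.

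**What to change.** 1. Amend the 6-week footnote in section 2 so that existing site staff check the patient's hospital records once, soon after day 90, for any AE or SAE from surgery to day 90.
2. In section 9.1.6, item 3, make the 6-month form prompt separately for (a) any AE or SAE, of any kind, that occurred up to day 90, and (b) AEs or SAEs of the ankle region after day 90. Dates come from the existing AE form, so no new date field is needed.

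The two parts complement each other. The record check brings forward what the hospital already knows, and the prompt reaches events treated elsewhere that its records may not show.

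No patient visit is added. The cost is a short record check per patient and one reworded form item. Reported AE counts may rise slightly because capture is better; that should be borne in mind in any comparison with a series that had no such check.
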